#### **Participants**

All local authorities in England were eligible to apply to take part in the trial. An initial call was made to the sector in January 2019, asking for applications, with a closing date of 8th February. Local authorities were selected on the basis of pre-set criteria: senior leadership support, ability to deliver the intervention, ability to facilitate randomisation and ability to support data collection. A second call was made to the sector in September 2019, asking for applications for phase two of the trial. Local authorities were selected on the basis of the same pre-set criteria. More details about the application process and the criteria can be found on the What Works for Children's Social Care website.

All members of staff in participating children's services departments are eligible to take part.

# **Sample Size Calculations**

		MDES (Proportion of a Standard Deviation)
MDES		0.23
	Child	n/a
Baseline/Endline Correlations	Family	n/a
	Social Worker	0.33
	Family	n/a
Intracluster Correlations (ICCs)	Social Worker	n/a
	Team	n/a
Alpha		0.05
Power	0.8	
One-sided or Two-sided?	One-sided	
Level of Intervention Clustering	Individual	
Average Cluster Size		n/a
Sample size of children's services	Intervention	238
staff, including social workers and others (without drop out	Control	238
adjustment)	Total	476
Sample size of children's services	Intervention	476
staff, including social workers and others (adjustment for 50% lost to follow-up)	Control	476
	Total	952
Sample size of children's services staff, including social workers and	Intervention	952
others (adjustment for 75% lost to	Control	952
follow-up)	Total	1904

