# Design

The overall study design is an individually randomised control trial with group delivery of the intervention. It is a two-arm study, with an intention-to-treat intervention group and a waiting-list control, with the aim of assessing the effectiveness of Schwartz Rounds within children's social care in relation to the psychological well-being of staff.

Trial Type and Number of Arms		Randomised control trial with two arms (intention-to-treat and waiting-list control)	
Unit of Randomisation		Individual members of staff	
Stratification Variables (if applicable)		Phase (one or two)	
Primary Outcome	Variable	Psychological well-being of staff	
	Measure (instrument, scale)	GHQ-12	
Secondary Outcome(s)	Variable(s)	Sickness-related absence	
	Measure(s) (instrument, scale)	Self-report	

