#### Where:

- $Y_{it}$  is the level of an outcome measure observed by participant I at time t (the T2 survey).
- α is a regression constant.
- $S_i$  is a binary indicator of treatment assignment, set to 1 if participants have been assigned to treatment, and 0 else.
- $Y_{it-1}$  is participant I's baseline score for the outcome measure.
- $X_i$  is a vector of participant level characteristics (gender, age, ethnicity, phase 1 or phase 2).
- $\epsilon_i$  is a Huber white robust standard error.

Where participants have T2 data but not T1 data,  $Y_{it-1}$  will be inputted as 0, and a binary variable contained within the vector X denoting that baseline data are missing will be set to 1 (else 0).

Secondary analysis will be considered using matched exclusion. For this analysis the model used will be identical to the main model, with the data used for the model having been subject to exclusion. Participants for exclusion will be matched on characteristics contained within X and on their baseline GHQ-12 data.

The sample size for the RCT was based on a one-sided hypothesis and this will be reflected in the reporting of the results of the primary analysis.

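### Group delivery is declared, but the sample size table and primary model make no allowance for correlation in the intervention arm; separately, the listed baseline correlation of 0.33 is not used

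*Protocol*

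**What the plan says.** The Design section states: "The overall study design is an individually randomised control trial with group delivery of the intervention". The table of changes at the front of the protocol records that the note on group delivery is new in this version, and that the sample size section was updated as well.

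The Sample Size Calculations table gives an MDES of 0.23 SD, alpha 0.05 one-sided, power 0.8 and 238 per arm before drop-out. The entry for "Level of Intervention Clustering" is Individual; the ICCs at family, social worker and team level and the average cluster size are all n/a. Under "Baseline/Endline Correlations" the table lists "Social Worker 0.33".

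The Primary Analysis is a linear regression of the T2 score on assignment, baseline score, gender, age, ethnicity and phase. Its error term "is a Huber white robust standard error". There is no term for authority or group, and no clustering of the errors. The same section adds: "The sample size for the RCT was based on a one-sided hypothesis".

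**The concern.** Intervention staff in an authority are invited to the same series of Rounds, with the same facilitators and storytellers. The Logic Model explains the effect through connectedness, trust and group interaction, and the Contextual Factors Analysis expects sites to differ in ways that could change effectiveness. On the protocol's own theory, some correlation among intervention-arm outcomes within an authority is plausible. Entering n/a amounts to assuming none.

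Huber-White errors deal with unequal variances. They do not deal with correlation between people who share a group. If that correlation is positive, the standard error of the treatment effect is too small and the primary test rejects too often. The bias favours declaring benefit, at a threshold that is already one-sided 5%.

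The unused 0.33 is a different matter. The model adjusts for baseline, so a reader would expect the listed correlation to have entered the calculation.

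**Working it through.** **Inputs from the protocol.** d = 0.23 SD; one-sided alpha 0.05 (z = 1.645); power 0.8 (z = 0.842); r = 0.33; 238 per arm; 11 authorities; 1:1 allocation within each authority's staff list.

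**Inputs assumed.** The protocol gives neither an ICC nor an analysed group size. I take 238/11 = 21.6 analysed intervention staff per authority, spread evenly, and an intervention-arm ICC of 0.01, 0.03 or 0.05.

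**1. The protocol's own figure.** n per arm = 2(1.645 + 0.842)²(1 − r²)/d².
- r = 0: 2 × 6.185/0.0529 = 233.8, so 234. At 238 per arm the SE is √(2/238) = 0.0917, the MDES is 2.487 × 0.0917 = 0.228, and power at 0.23 is Φ(0.23/0.0917 − 1.645) = 0.806. This matches the table to rounding.
- r = 0.33: 1 − r² = 0.8911, giving 209 per arm. At 238 per arm the MDES is 0.215 and power is 0.844.
- The drop-out rows follow: 238/0.5 = 476 and 238/0.25 = 952.

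So 238 is correct for an unadjusted, unclustered, one-sided comparison, and 0.33 was not used.

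**2. One-sided error with unclustered standard errors.** The intervention-arm design effect is DE = 1 + (21.6 − 1) × ICC. The variance of the treatment contrast is inflated by VIF = (1 + DE)/2, because only one arm is clustered. The true error is 1 − Φ(1.645/√VIF).

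| ICC | DE | VIF | True one-sided error |
|---|---|---|---|
| 0.01 | 1.206 | 1.103 | 5.9% |
| 0.03 | 1.619 | 1.310 | 7.5% |
| 0.05 | 2.032 | 1.516 | 9.1% |

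r cancels from this ratio, so the unused correlation has no effect on the error.

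**3. Allowing for authority differences common to both arms.** Randomisation is within authority, so these differences cancel from the contrast but still enlarge the unclustered standard error. With a shared ICC of s, VIF becomes 1 − s + (21.6 − 1) × ICC/2. For s = 0.05 (assumed) this is 1.053, 1.260 and 1.466, giving errors of about 5.4%, 7.1% and 8.7%.

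**4. Power with correct standard errors, normal approximation.** SE = √[(1 − r²)(1 + DE)/238]. With r = 0.33 the SE is 0.0909, 0.0990 and 0.1065, so the MDES is 0.226, 0.246 and 0.265, and power at 0.23 is 81%, 75% and 70%. Power is exactly 80% when 1 + DE = 238 × 0.0529/(6.185 × 0.8911) = 2.285, that is ICC = 0.285/20.6 = 0.014.

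**5. Power with the degrees of freedom the design allows.** A model with authority fixed effects and an intervention-arm authority effect rests on 11 within-authority differences, hence about 10 df (balanced case; critical value 1.812). Using the non-central t distribution and the SEs of step 4:

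| ICC | MDES | Power at 0.23 |
|---|---|---|
| 0.01 | 0.243 | 76% |
| 0.03 | 0.265 | 70% |
| 0.05 | 0.285 | 64% |

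**The case against.** A reader might infer that the stated 80% power and 5% error are simply not what this trial delivers. The protocol does not support that, for four reasons.

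- **The size of the problem is assumed.** No ICC or analysed group size is given. If group delivery induces no correlation, the error is 5%.
- **The two omissions pull in opposite directions on power.** Leaving out 0.33 is conservative and absorbs an ICC of up to about 0.014 at 21.6 per authority; with 10 per group the figure is about 0.032. Setting r aside is also defensible, because responders without T1 data stay in the model with baseline set to zero and a missing indicator, so 0.33 does not apply to everyone analysed.
- **The clustering may be weak.** Attendance is optional, the process evaluation expects non-attenders and irregular attenders, and virtual Rounds are for smaller groups. Under intention to treat, if a fraction p attends, an ICC among attenders contributes roughly p² times its value: 0.05 with p = 0.5 (both assumed) gives about 0.0125.
- **Randomisation within authority removes shared authority effects.** Step 3 of the working shows the modest offset.

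All of this stands against the flat claim. It does not justify n/a. Dilution and offset argue for stating a range. The correlation offset protects power only, never the error rate, and under about 10 df power is already 76% at an ICC of 0.01.

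**Conclusion.** The point holds conditionally. Group delivery is declared, but the table and the primary model both ignore it, and both are fixed in the protocol. For any material positive intervention-arm ICC the one-sided error exceeds 5%: about 5.9% to 9.1% over ICC 0.01 to 0.05 with 21.6 analysed per authority, and about 5.4% to 8.7% if a shared authority ICC of 0.05 is also present. Attendance-driven dilution would move a trial towards the lower end.

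The unused 0.33 is a reporting gap, not a cause of lost power: applied to the table's own unclustered inputs it would give 209 per arm, or 84% power at 238. It should not be read as part of the error-rate problem. Nor does the protocol show that the trial is underpowered as it stands, since that depends on an ICC it does not give.

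**What to change.** 1. **Primary model.** Replace the plain Huber-White errors with a partially nested model: authority fixed effects, plus an authority-level random effect in the intervention arm only, with Satterthwaite or Kenward-Roger degrees of freedom. Authority fixed effects replace the phase term, since phase is constant within an authority and the two cannot both be fitted.
2. **Sample size table.** Replace Individual and n/a with intervention-arm clustering by authority. State an assumed ICC range and the analysed group size. Say whether 0.33 is used, noting that it applies only to responders with T1 data. Restate MDES and power with the same small-sample degrees of freedom as the model. With r = 0.33 for everyone, 238 per arm and about 10 df, the entries would be an MDES of about 0.243 / 0.265 / 0.285 and power at 0.23 of about 76% / 70% / 64% for ICC 0.01 / 0.03 / 0.05. The normal-approximation figures in step 4 should not be printed beside a model with about 10 df.

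**Cost.** Edits to one table and to the primary model, including its covariate list. The interval becomes moderately wider and the stated MDES less favourable. No extra recruitment is needed. Phase one data are already collected, so the change should be recorded before outcomes are compared by arm.

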#### **Outcome measures**

Our primary outcome is the psychological well-being of children's services staff. The main secondary outcome is the amount of sickness-related absence. The primary outcome will be measured using the GHQ-12, administered at T1 (prior to the start of the intervention) and at T2 (which should be after four to six rounds have been provided, however for phase two, T2 will take place in March and April 2021 irrespective of how many rounds have been completed by that stage. The secondary outcome will be measured using self-report data collected as part of T2 (we previously intended to collect sickness-related data directly from LAs, however in phase one, none of the LAs were able to provide this data in relation to their staff groups, hence we will now rely on self-report data instead).

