Cost evaluation (p. 18)	Additional information added about how we will consider any differences in cost between face-to-face and virtual rounds.
Data protection (p. 19)	Added in a link to Cardiff University's data protection notice for research participants.
Personnel (p. 19)	[name] joined the research team in March 2020.
Timeline (p. 19-20)	Amended to reflect the addition of five new authorities and revised dates for data collection and the end of the project.
References (p. 21)	Additional references added.

Working in children's services is challenging, with workers often reporting high levels of stress and 'burn out'. Such difficulties can contribute to high rates of sickness-related absence and turnover (Ravalier, 2018). Recent Department for Education (2019) figures indicate a headcount turnover rate of 16% in the year ending September 2018, compared to a turnover rate for teachers of 9% over a similar period. Previous research has shown that the expected working life for a social worker is eight years, compared with twenty-five years for doctors and fifteen years for nurses (Curtis et al, 2010). Levels of stress may be exacerbated by limited resources, high workload and insufficient organisational support. Yet even in ideal circumstances children's services would still be a stressful place to work. Social workers and others will regularly encounter people living in very difficult situations, who have experienced abuse, neglect, poverty and social exclusion. Helping staff to provide the best possible levels of service means taking account of the nature of the work itself, and how it can create stressful emotional responses.

Schwartz Rounds is an intervention aimed at improving the psychological well-being of staff and improving the nature of care provided. There is some evidence that it works in health settings. This study will evaluate whether it improves psychological well-being and reduces staff stress in English children's services.

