#### Secondary hypotheses are:

[figure not shown]
- a. The proportion of GHQ-12 scores above the 'caseness' threshold (of 3) will be lower in the intervention group than in the control group at T2.
- b. The number of days of sickness-related absence during the trial period will be lower in the intervention group than in the control group at T2.
- c. Regular attendance at Schwartz Rounds will be associated with lower GHQ-12 scores compared with less regular and non-attendance.
- d. Schwartz Rounds will be considered acceptable by the staff who attend.

We will also conduct some other exploratory analyses described in the analysis plan.

[figure not shown]

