#### **Data collection points**

T1 data collection (GHQ-12 plus additional questions about personal and professional characteristics, views about the intervention and current forms of emotional support) will be collected electronically via Qualtrics. Links to the survey will be sent to members of children's services staff at participating sites. Participants will be asked to include their initials and day and month of birth and/or their work email addresses, so that T1 responses can be linked with sessional feedback questionnaires (see below) and T2 questionnaire responses. Raw data will be downloaded from Qualtrics to a secure Cardiff University computer for analysis via SPSS or STATA. Data from each of the participating sites will be merged together into a single database.

T2 data collection (GHQ-12 plus additional questions about other forms of emotional support utilised within the trial period and views about the intervention) will be collected in the same way as T1 data.

To minimise missing data at T1 and T2, we will work with the Local Authority sites to ensure good communication with participants and ask that two follow-up reminders are sent to participants who do not complete the surveys after the first request. We will follow up any still-missing participants directly with the LA (i.e., they will be informed of participants who have not responded and asked to send a third follow-up request). We will also offer an incentive for completing the surveys at T1 and T2, entering each participant who does so into a draw to win £250, with one winner selected from each LA (Nb. One of the local authorities in phase one – Liverpool – opted out of this prize draw).

Anonymised versions of the entire dataset will be stored at Cardiff University for five years after publication of findings.

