# **Ethics & Participation**

Ethical approval for the study has been given by the School of Social Sciences, Cardiff University.

Staff in participating local authorities will be given information and consent sheets about the study. Each local authority will then implement an individual communication strategy, to ensure staff are aware of the intervention, involving a mixture of email bulletins, intranet blogs and staff briefing sessions. Written consent will be obtained from each attendee at each Schwartz Round (to ensure that irregular attendees, who may not have attended the first round or any round before, are also given the opportunity to consent or not). This will be done as part of the sessional feedback questionnaire. Questionnaires will be given out to each member of staff upon arrival at the round by one of the facilitators or the Practice Lead. At the end of each round, staff will be reminded to fill in the questionnaire and return it to the facilitators on their way out. If staff have already completed a consent form, they will not need to fill in another one on subsequent rounds but may choose to do so as part of completing the feedback questionnaire.

Each member of staff in the department will also be emailed a T1 and T2 questionnaire (including the GHQ-12). Completion of the questionnaire will be voluntary. This will be made clear in the invitational email and at the start of the questionnaire itself.

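### Sickness absence is known only for staff who answer the T2 work survey, so hypothesis b is likely to be missing depending on its own value, with a bias whose direction is not fixed

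*Protocol*

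**What the plan says.** Hypothesis b reads: "The number of days of sickness-related absence during the trial period will be lower in the intervention group than in the control group at T2". Under Outcome measures the data source is fixed: "The secondary outcome will be measured using self-report data collected as part of T2". The reason given is that in phase one "none of the LAs were able to provide this data in relation to their staff groups". The summary of changes adds that retention data could not be collected either, and that retention was dropped as an outcome.

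Ethics & Participation sets the route: "Each member of staff in the department will also be emailed a T1 and T2 questionnaire", and "Completion of the questionnaire will be voluntary". Under Data collection points the team will "ask that two follow-up reminders are sent to participants who do not complete the surveys after the first request". For those still missing, the authorities come in: "they will be informed of participants who have not responded and asked to send a third follow-up request". There is also a prize draw. No step is aimed at staff on sick leave or staff who have left.

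The sample size table allows for 50% and 75% loss to follow-up. Under Randomisation, each authority receives the allocation list in a form it can re-identify, staff learn their group after T1 closes, and analysts are blinded for GHQ-12 and group-level absence data.

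**The concern.** Hypothesis b counts days absent over the whole trial period, but the count exists only for people who answer a work survey at the end of it. Someone on long sick leave during the T2 window has many days to report and is less likely to read work email. Reminders sent by the same route do little for that person. Someone who left because of ill health may no longer be reachable at all. The chance of observing the outcome then depends on the outcome.

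This matters most if Rounds act on long absences, because a few such staff can hold a large share of all days absent. It also matters if the two arms lose these staff at different rates, because a difference could then appear where none exists. Nothing in the plan records how many randomised staff were off sick or gone at T2, so the report could not show which situation applied. An analysis plan written later could not recover a count that nobody had collected.

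**Working it through.** **The plan's own figures.** The protocol states no figure for absence. Its loss-to-follow-up rows reproduce exactly: 238/(1-0.50) = 476 and 238/(1-0.75) = 952 per arm. They show that heavy non-response is expected, but they concern the GHQ-12.

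**Step 1: equal loss, effect confined to long absence.** All inputs are assumed: 3% of controls and 2% of intervention staff are off sick at T2 with L = 60 days each (range 40 to 90), and everyone else has 3 days.

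- True difference = (0.02 - 0.03) x (L - 3) = -0.37, -0.57 and -0.87 for L = 40, 60 and 90.
- Off-sick share of control days = 0.03L/(0.03L + 0.97 x 3) = 29%, 38% and 48%.
- If off-sick staff answer at a fraction f of the usual rate, the observed mean is (p f L + (1-p) x 3)/(p f + 1 - p). At L = 60:
  - f = 0.5: intervention 3.54/0.990 = 3.576, control 3.81/0.985 = 3.868, difference -0.29.
  - f = 0.25: intervention 3.24/0.985 = 3.289, control 3.36/0.9775 = 3.437, difference -0.15.
  - f = 0: 3 in both arms, difference 0.

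**Step 2: unequal loss, no true effect.** Put 3% off sick in both arms with L = 60. If f = 0.5 in control and 0.25 in intervention, the observed difference is 3.437 - 3.868 = -0.43, a false benefit. With the fractions exchanged it is +0.43.

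**Step 3: response falling smoothly with days absent, alike in both arms.** This was simulated with 2 million staff per arm. Assumed inputs: negative binomial days with means 6 and 4.8, dispersion k of 0.3 or 0.6, base response 25% or 50%, and log-odds of response falling by 0.02 to 0.10 per day absent. The observed difference was 0.14 to 0.81 of the true one. With no dependence on days the ratio was 1.00 to 1.04.

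**Step 4: where the effect lies and who is lost.** This was also simulated with 2 million per arm. Assumed inputs: short absence averaging 5 days, 3% of controls with a further 20 to 120 days, and totals capped at 150. In the intervention arm the short mean falls to 4, or the long-absence share falls to 2% (2.4% when both are reduced by a fifth). Entries are differences in mean days.

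| Effect lies in | True | All long-absent lost, both arms | 80% lost in control, 40% in intervention | 40% lost in control, 80% in intervention |
|---|---|---|---|---|
| long absence only | -0.72 | -0.01 | +0.41 | -1.00 |
| short absence only | -0.99 | -1.00 | -0.16 | -1.84 |
| both, by 20% | -1.43 | -1.00 | -0.42 | -1.94 |
| neither | -0.01 | -0.01 | +0.82 | -0.85 |

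The -0.01 in the last row is simulation noise around zero. With equal loss, the bias runs from none to complete. With unequal loss, the sign itself is open.

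**The case against.** **Forced choice.** Self-report is an openly stated fallback for records that could not be obtained, and it concerns a secondary outcome. That is fair. The point is not that self-report should have been avoided, but that what it loses can be counted.

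**The loss is inferred.** T2 ran over January and February 2020 in phase one. In phase two it is set for March and April 2021 (the Timeline says April), with up to three follow-up requests. Only leave that spans the window, or work email left unread, removes someone, and staff back from a long absence can report it. This stands, and it is why partial response is shown as well as none.

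**Direction.** A reader might infer that hypothesis b must be pulled toward no effect. The documents do not support that. The zero in step 1 follows from placing the whole effect in the group assumed silent. If the effect lies in short absences there is no shift, and because staff know their group before T2, equal loss cannot be assumed.

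**Consequence.** A reader might also blame selection for a non-significant result. With step 1's inputs and 238 analysed per arm, the true difference over its standard error is 0.01/sqrt((0.03 x 0.97 + 0.02 x 0.98)/238) = 0.70. One-sided power at 0.05 is then about 17%, even ignoring all other variance. Complete data would usually miss such an effect too. The issue is bias in the estimate.

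**Turnover and savings.** The Background cites "a headcount turnover rate of 16% in the year ending September 2018". This is all-cause turnover from a social work workforce source. It does not measure sickness-related leaving in this trial and enters no calculation here. Nor does the bias carry straight into the savings estimate: Cost Evaluation bases savings on administrative absence and retention data. That sits badly with Outcome measures, but it is a separate matter.

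**Analysis plan.** Handling of missing T2 outcomes may be set out in an analysis plan not seen here, and its absence from the protocol is not held against it. Collecting the counts is a protocol matter.

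**Conclusion.** The concern holds in a conditional form. Days absent are likely to be missing depending on their own value, because the only source is a voluntary emailed work survey at the end of follow-up. The bias is toward zero if loss is alike in both arms and any effect includes long absences. It is about nil if the effect lies only in short absences and loss is alike. It can go either way, including a false benefit, if loss differs by arm.

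The documents give no absence distribution and no response rate among staff off sick, so the size is unknown. The figures above show what is possible on assumed inputs and are not estimates for this trial. Because the direction cannot be settled in advance, the counts by arm are worth having. This is a moderate point about a secondary outcome, and it can still be acted on for phase two, whose T2 falls after this December 2020 version.

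**What to change.** 1. **Count.** At the existing contact with each phase two authority about non-responders, ask for an aggregate count by allocated group of staff in post, off sick and left at the close of T2. Use coded group labels so that analysts stay blinded. Report the counts over all randomised staff beside hypothesis b.
2. **Wording.** Keep hypothesis b as the comparison of the randomised groups, and state that its estimate comes from T2 responders. Do not redefine it as absence among staff at work and responding, since that conditions on status after randomisation.
3. **Sensitivity analysis.** Return off-sick non-responders to each arm over a stated range of days, up to the full length of follow-up. Let the share of off-sick staff who answered differ by arm.
4. **Where counts are missing.** For authorities that cannot supply them, and for phase one, where collection is complete, run the same analysis over a stated range of assumed proportions.

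The cost is some protocol wording, one aggregate request to five authorities at a contact already planned, and one extra analysis. The downside is that some authorities may not supply the count, since absence and retention data could not be obtained before. The six phase one authorities may be covered by assumption only.
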